The New Zealand National Science Challenge High Value Nutrition (NSC-HVN) programme aims to identify established and novel blood, urine and faecal biomarkers related to increased risk of type 2 diabetes (T2D); and in turn to undertake nutrition interventions that target these biomarkers and thereby decrease T2D progression in high risk individuals. Tranche 1 of the HVN Peak Nutrition for Metabolic Health (PANaMAH) Programme investigated susceptibility to T2D in 'at risk' individuals even at a low body mass index (BMI) and hence outwardly lean. This is likely due, at least in part, to deposition of storage fat in 'risky' central sites such as visceral adipose depots and the non-adipose ectopic sites of pancreas and liver. This has been termed the *thin-on-the-outside-fat-on-the-inside* or 'TOFI' profile.

Tranche 2 of the PANaMAH programme will investigate nutrition interventions to ameliorate T2D risk in carefully phenotyped lean and overweight individuals with pre-diabetes resident in New Zealand. Recent studies have shown that greatest success in improving metabolic health, including euglycaemia, can be achieved when long-term dietary intervention for improved glycaemic control is preceded by prior body weight and adipose mass loss achieved through the use of a low energy diet (LED) and subsequent suppression of weight re-gain (Astbury et al., 2018; Christensen et al., 2018; Lean et al., 2018). Identifying dietary components that can contribute to this long-term weight loss maintenance and hence improve glycaemic endpoints is key to this. In addition, evidence is building in support of personalised diets where glycaemic response to intervention may be predicted through integration of factors such as dietary intake, continuous glucose monitoring, serum metabolome and faecal microbiome (Korem et al., 2017; Thaïss et al., 2016; Valsesia et al., 2020; Zeevi et al., 2015). Previously the PANaMAH programme has focused on shorter-term dietary/food and beverage (F&B) intervention studies of up to 3 months, in small cohorts of up to 120 individuals, with no weight loss component and a 'one-size-fits-all' diet approach.

The FERDINAND Study builds on the previous PANaMAH programme, and significantly extends into a longer-term 6 month intervention in a larger multi-ethnic cohort of 'at risk' adults; with the aim of evaluating a F&B product that may contribute to improved glycaemia during both weight/adipose mass loss and longer-term weight loss maintenance. Plant-derived polyphenols, commonly found in fruits such as feijoa, may provide a novel nutrition approach with evidence from prior pre-clinical, and a human clinical study, demonstrating improvement in glycaemic parameters following short-term consumption of 150 mg/d commercially available whole feijoa powder. Use of machine-learning algorithms will integrate clinical responses and 'omics outputs to predict individual response to the intervention, and will include quantitative measurements of personalised postprandial glucose response (PPGR) to determine between-individual variability, and identify baseline parameters that predict this variability. The outcomes of PPGR from the FERDINAND Cohort, following 6 months consumption of feijoa whole fruit powder, will provide predictive algorithms that can be validated in a future follow-up assessment.

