2. STUDY OBJECTIVE

The objective of this study is to investigate the long-term effects of whole fruit feijoa powder, both during and following LED-driven weight loss on established and novel biomarkers of T2D, using an integrated systems nutrition approach; in a parallel design, RCT of 6 months duration, in a high risk multi-ethnic population with pre-diabetes resident in New Zealand.

Also, to develop a machine-learning algorithm that predicts PPGR in a sub-cohort of participants undergoing the longitudinal 6-month intervention; so that the predictive PPGR algorithm can be tested in a future study.

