3. METHODS

3.1 TRIAL DESIGN

The trial will be a 2 arm, parallel design, double blind RCT. The dietary intervention will span 6 months, consisting of an initial acute 2-month weight-loss driven by LED (Phase 1) and followed by a longer-term 4-month weight loss maintenance (Phase 2).

The 2 intervention arms are as follows:

[figure not shown]
1. Healthy diet/weight loss advice + feijoa whole fruit powder

Total meal replacement during the LED phase only (e.g. CID1-CID2), 4MJ/day; 1150 mg/d feijoa whole fruit powder daily in both phase 1 and phase 2 (to be consumed daily, with breakfast meal)

2. Healthy diet/weight loss advice + matched Placebo

Total meal replacement during the LED phase only (e.g. CID1-CID2), 4MJ/day; 1150 mg/d matched placebo (e.g. bland non active commercial placebo like microcrystalline cellulose) daily in both phase 1 and phase 2 (to be consumed daily, with breakfast meal)

FIGURE 1. INTERVENTION ARMS

▲ Fading visit design; clinical investigation days (CIDs) and group diet advice (combination of in-clinic and virtual/online sessions); LED - wks 0, 2, 4, 6, 8 (5 time points); Maintenance - mths 3, 4, 5, 6 (4 time points)

LED, low energy diet (4MJ/day): total meal replacement provided as sachets (Cambridge Weight Plan™ Ltd)

Body weight and composition (by dual energy x-ray absorptiometry, DXA) at CID 1/baseline, CID 2/end of LED, CID 3/4months & CID 4/end of study.

Magnetic resonance Imaging and Spectroscopy (MRI/MRS, sub-group, n=30; n= 15 placebo arm and n=15 whole fruit powder arm) assessment [7 day window] at CID 1/baseline, CID 2/end of LED, CID 4/end of study

Continuous glucose monitoring (CGM) over 4 days, for postprandial assessment incl. 2h OGTT and mixed (breakfast) meal tests; at CID 1/baseline all participants, CID 2/end of LED (sub-group; n= 40 placebo arm and n=40 whole fruit powder arm), CID 4/end of study (sub-group; n= 40 placebo arm and n=40 whole fruit powder arm)

[figure not shown]
Indirect calorimetry (IC) in a subgroup of n = 30 (n = 15 placebo arm and n = 15 whole fruit powder arm) measured during 2h OGTT at CID 1/baseline, CID 2/end of LED, CID 4/end of study

CHARACTERISATION OF BASELINE PHENOTYPE – IDENTIFYING PREDICTORS OF PPGR

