Demographic, anthropometric, clinical, metabolome and microbiome parameters will be integrated into an algorithm to predict PPGR, based on the methods developed in a cross sectional study of postprandial glucose control (Zeevi et al., 2015). Specifically, the PPGR for each participant will be predicted using a model developed from demographic (including ethnicity), anthropometric (including DXA, MRI and MRS), CGM including individualised postprandial OGTT and MMT responses, clinical, serum metabolome and faecal microbiome markers collected at the respective study visits.

CGMs are designed for self-insertion in home settings by individuals. For example they are routinely used by individuals with diabetes who need to monitor their blood glucose (<https://www.mediray.co.nz/diabetes/shop/freestyle-libre-flash-glucose-monitoring-system/freestyle-libre-flash-glucose-monitoring-system>). CGMs will be inserted under the skin; participants will be provided with the protocol and additionally guided/supported through the process on a video call, to allow continuous assessment of blood glucose levels throughout a 4-day period. If participants are uncomfortable doing this themselves then our study nurse will do this at the Human Nutrition Unit (HNU). Physical activity (PA) will also be assessed using a step count on mobile phone GPS technologies (e.g. Apple 'health' app) or simple pedometer if smart phone is not available. On Days 1-3 CGM assessments will be conducted at the participant's home and on Day 4 they will attend the HNU clinic for additional assessments (Figure 2).

FIGURE 2: 4-DAY PROTOCOL OF 3 MMTs CONSUMED AT HOME (1 PER DAY) AND AN ORAL GLUCOSE TOLERANCE TEST (OGTT) ON DAY 4 IN CLINIC.

MMT mixed meal test; OGTT, oral glucose tolerance test (plus IC, indirect calorimetry, in sub-group)
Physical Activity (PA), step count using mobile phone GPS technologies (eg. Apple 'Health' app)

On Day 1-3 of the home CGM assessment, a MMT will be conducted, which requires the participant to consume a single standardised breakfast meal at a fixed time on each of the 3 days. At the HNU clinic, on Day 4, an OGTT will be conducted (Figure 2) following the standard World Health Organisation (WHO) protocol with CGM and repeat venous blood sampling following cannulation and IC. CGM recordings will then be analysed to determine individual glycaemic response to the standardised meal.

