The postprandial CGM assessments will be conducted prior to the start of the LED, i.e. 3 days prior to CID1/baseline visit in all participants; and similarly 3 days prior to CID4/8 months but only in the sub-group of participants randomised to the placebo and the feijoa whole fruit powder intervention arms (40 participants each arm; Table 1).

WEIGHT LOSS_LOW ENERGY DIET [LED]: PHASE 1

Commercial LED meal replacements (Cambridge Weight Plan™ Ltd) will be consumed for 8 weeks throughout Phase 1. LED is energy restricted with a target intake of ~4MJ/day. The target macronutrient composition of the diet will be 15-20% of total energy from fat, 35-40% from protein and 45-50% from carbohydrate. LED products include shakes, soups, bars, porridge, pasta and savoury meals.

- Participants randomised to the Healthy diet/weight loss advice + feijoa whole fruit powder arm will receive the LED products to be consumed as a total meal replacement with the whole fruit powder to be supplemented into the diet and consumed alongside the LED, with target EI of 4MJ/day.
- Participants randomised to Healthy diet/weight loss advice + matched Placebo arm will receive the LED products to be consumed as a total meal replacement with the matched placebo to be supplemented into the diet and consumed alongside the LED, with target EI of 4MJ/day.

During Phase 1 participants will attend, either in person or via virtual online mHealth platform, 5 group meetings delivered from the HNU clinic site. At each group meeting, adverse events (AE) and concomitant medications will be recorded; and dietary advice and behavioural instructions provided by dietitians. Participants will be recommended to maintain PA as per baseline (no increase) during the LED weight-loss phase. All participants will remain on the LED until their CID2 visit at week 8. It is expected that weight loss over 8 weeks will be between 5-10% of baseline body weight.

WEIGHT MAINTENANCE_DIETARY INTERVENTION: PHASE 2

During Phase 2 (4 months) participants will attend, either in person or via virtual mHealth platform, 4 group meetings delivered from the research site. The dietary advice will adhere to the New Zealand Ministry of Health healthy eating guidelines (McIntyre & Dutton, 2015) for improving metabolic health, with diet advice provided by dietitians.

CLINIC ASSESSMENTS

TABLE 1. SUMMARY OF CID ASSESSMENTS OVER THE 6 MONTH STUDY PERIOD

Assessments	Phase 1 - LED		Phase 2- Maintenance	

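### The protocol gives the prediction algorithm inconsistent targets, names no placebo contrast for individual response, and contradicts itself on whether placebo participants have the end-of-study mixed meal test

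*Protocol*

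**What the plan says.** **Target.** The introductory summary (paragraph on the FERDINAND Study, before section 1) says the machine-learning work is "to predict individual response to the intervention, and will include quantitative measurements of personalised postprandial glucose response (PPGR) to determine between-individual variability". It then names the source of the algorithm: "The outcomes of PPGR from the FERDINAND Cohort, following 6 months consumption of feijoa whole fruit powder, will provide predictive algorithms". Placebo is not mentioned there.

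Section 2 (Study Objective) states the aim differently, as an algorithm that "predicts PPGR in a sub-cohort of participants undergoing the longitudinal 6-month intervention", without saying which arm or arms. Section 3.1, under the heading on baseline phenotype and predictors of PPGR, says that "the PPGR for each participant will be predicted using a model developed from demographic (including ethnicity", followed by anthropometric, CGM, clinical, metabolome and microbiome markers. Randomised arm is neither listed nor excluded. The method is said to follow a cross-sectional study.

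**Common treatment.** Section 3.1 describes an "initial acute 2-month weight-loss driven by LED (Phase 1"). The placebo arm is described as "Total meal replacement during the LED phase only (e.g. CID1-CID2), 4MJ/day; 1150 mg/d matched placebo", and the Phase 1 text adds "All participants will remain on the LED until their CID2 visit at week 8". Expected weight loss in that phase is 5-10% of baseline body weight.

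**Placebo follow-up.** The Figure 1 notes, the paragraph just before Phase 1 and Table 1 all plan month-6 meal tests with CGM in 40 placebo and 40 powder participants. Table 1 and the Visit 7 list plan the month-6 OGTT in the same numbers. The Visit 6 list, however, restricts the end-of-study three-day MMT to the powder group.

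**The concern.** In a parallel-group trial nobody is seen under both treatments. A powder recipient's month-6 value, or change from baseline, mixes any powder effect with the LED effect, the person's underlying prognosis, regression to the mean and measurement error. Markers that predict that value are prognostic. They show who responds to powder only if they predict the difference from placebo.

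The summary's wording invites the stronger interpretation: it speaks of individual response and ties the algorithm to PPGR after feijoa. If the model were built on powder recipients alone, baseline markers would appear to predict response even with an inert powder, and that result would go forward to the later validation. If the Visit 6 list is followed, the placebo MMT data needed to check this would not exist, and no analysis plan written later could recover them.

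**Working it through.** **1. The protocol's own figure.** The only sample-size calculation is for fasting plasma glucose: difference 0.3 mmol/L, SD 0.6, alpha 0.05, power 80%, dropout 20%.
- Normal approximation, two-sided: n = 2 × (1.960 + 0.842)² × (0.6/0.3)² = 62.8, so 63 per arm. The noncentral t gives 64 (power 0.8015).
- Dropout: 64 / 0.80 = 80 per arm.

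The stated 64 and 80 reproduce. This calculation does not cover the prediction work, and no calculation for the algorithm is given.

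**2. What baseline explains when the powder does nothing.** Let B and F be the baseline and month-6 values of one glucose measure, with equal variance σ² and correlation ρ. The documents give no ρ and no PPGR SD, so ρ = 0.4 to 0.8 is assumed.
- Change score C = F − B: Cov(B, C) = −(1 − ρ)σ² and Var(C) = 2(1 − ρ)σ², so R² = (1 − ρ)/2.
- Month-6 level F: R² = ρ².

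| ρ (assumed) | R² for change, (1 − ρ)/2 | R² for level, ρ² |
|---|---|---|
| 0.4 | 30% | 16% |
| 0.5 | 25% | 25% |
| 0.6 | 20% | 36% |
| 0.7 | 15% | 49% |
| 0.8 | 10% | 64% |

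An LED fall common to everyone shifts the mean and leaves these figures unchanged. Varying LED response between people is not quantified here.

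For the change score, leave-one-out R² in simulated arms of 40 averages about 0.23 at ρ = 0.4, 0.13 at ρ = 0.6 and 0.02 at ρ = 0.8. Cross-validation therefore does not remove the artefact at the lower correlations and nearly does at the highest.

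**3. Powder arm alone against a placebo contrast.** This uses 4,000 simulated trials for each ρ, with 40 per arm, no powder effect and the same LED fall in both arms. The first column is how often baseline predicts change at p < 0.05 in the powder arm alone. The second is how often an arm-by-baseline term fitted to both arms is significant.

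| ρ (assumed) | Powder arm alone | Arm-by-baseline term |
|---|---|---|
| 0.5 | 92% | 5.0% |
| 0.6 | 84% | 5.3% |
| 0.7 | 71% | 4.8% |
| 0.8 | 53% | 5.9% |

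The contrast brings the false-positive rate back to about the nominal 5%.

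**4. What the contrast can detect.** At 80% power and two-sided alpha 0.05, for one marker:
- Difference in slope per SD of the marker: 2.80 × √(2/40) = 0.63 residual SD. With 32 per arm after 20% dropout, 2.80 × √(2/32) = 0.70.
- Marker split at its median (20 per cell): 2.80 × √(4/20) = 1.25 SD. With 16 per cell, 2.80 × √(4/16) = 1.40 SD.

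**5. The schedule, side by side.**

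| Place in protocol | End-of-study MMT |
|---|---|
| Figure 1 notes | 40 placebo + 40 powder |
| Paragraph before Phase 1 | 40 in each arm |
| Table 1 | 40 placebo + 40 powder |
| Visit 6 list | powder group only |

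The month-6 OGTT is not in dispute: Table 1 and Visit 7 both give 40 per arm.

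**The case against.** The strongest reply is that the protocol does not commit to a powder-only analysis. A reader might infer that placebo is left out of the model. The text does not say so: placebo CGM follow-up is scheduled in 40 participants in most places, and arm terms and interactions may properly be left to an analysis plan. That stands.

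A reader might also infer that the algorithm is bound to learn regression to the mean. That is too strong. Sections 2 and 3.1 target PPGR, a response to a meal, and define no change score, so (1 − ρ)/2 applies only if change is modelled. Nor is PPGR one value per time point: three meal tests and an OGTT are planned at baseline. Selection is on fasting glucose at screening, a different measure and visit, so its bearing on PPGR is indirect.

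Nor does the protocol say the algorithm will be used to choose who benefits from feijoa. It says only that it "following 6 months consumption of feijoa whole fruit powder, will provide predictive algorithms that can be validated in a future follow-up assessment".

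Finally, the intervention may mean the whole LED-plus-maintenance programme. That reading is open, but it does not rescue the claim: everyone receives the LED, so the trial has no control for the programme, and randomisation identifies only the powder's effect. A PPGR-level model does not escape either, since baseline predicts the level whether or not the powder works.

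The mismatch between the summary and sections 2 and 3.1, and the conflict over the Visit 6 MMT, are protocol text and remain.

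**Conclusion.** The point holds in limited form. The summary promises prediction of individual response and sources it from PPGR after feijoa, while sections 2 and 3.1 describe predicting PPGR with inputs that omit arm. Taken as written, none of these separates response to the powder from the LED effect, prognosis or regression to the mean. With an inert powder, baseline alone would explain 30% to 10% of a change score, or 16% to 64% of the month-6 level, for ρ from 0.4 to 0.8. These figures rest on the assumed ρ, equal variances and a single glucose measure; they show what could be mistaken for response and do not forecast the trial's result.

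The contradiction over the end-of-study MMT needs no assumption and is the more urgent part, because placebo data not collected cannot be recovered. The algorithm is not itself listed among the co-primary or secondary outcomes, so the trial's main comparison is unaffected.

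**What to change.** 1. **Align the target.** State one target for the algorithm in the introductory summary, section 2 and the PPGR text of section 3.1.
2. **Reconcile the schedule.** Bring the Visit 6 list and the Figure 1 notes, the paragraph before Phase 1 and Table 1 into agreement on who has the end-of-study MMT, before month-6 visits take place. If response to powder is the target, placebo MMT data are needed.
3. **Choose the claim.** Either:
   - define response to the powder as a contrast with placebo, using both sub-groups of 40, with arm-by-feature terms or separate arm models and their predicted difference, and run the identical pipeline in the placebo arm as a negative control, claiming only what exceeds it; or
   - reword the claim to predicting PPGR and drop response to the intervention.

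**Cost.** The wording and analysis changes are nearly free. If sites have been working to the Visit 6 list, the placebo MMTs are additional to what is being done there, though already planned elsewhere in the protocol. The scientific cost is a weaker claim: with 40 per arm only a slope difference of about 0.63 residual SD per marker SD is detectable (0.70 after 20% dropout), before any allowance for screening many markers.

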1. BACKGROUND

Type 2 diabetes - a global health concern

Worldwide diabetes and adverse metabolic health greatly contribute to the healthcare and economic burden, with over 90% of those diagnosed with diabetes classified as type 2 diabetes (T2D) (Zheng, Ley, & Hu, 2018). The prevalence of T2D has dramatically escalated from 110 million people reported in 1994, to > 350 million in 2013, and is predicted to further increase to > 600 million by 2040 (Ogurtsova et al., 2017). This metabolic disorder is responsible for the death of approximately 1.5 million people annually and is a major risk factor for cardiovascular disease (CVD), in turn killing 13 million people worldwide each year and accounting for ~25% of all-cause mortality (Lozano et al., 2012). New Zealand is no exception to these trends with the number of individuals with T2D having more than doubled in recent years, with >200,000 individuals with this metabolic disease (Beig, Khanolkar, & Cundy, 2018; MinistryofHealth., 2016). The rapid uptrend of T2D globally will lead to it being the 7th leading cause of death by 2030 (NCDRiskFactorCollaboration, 2017).

T2D is not only a health concern for Westernised nations such as Europe, North America and Oceania, but recent evidence shows increasing prevalence in developing Asian countries as well (Alberti & Zimmet, 2014); particularly China where T2D prevalence has been estimated to reach close to 70% by 2030 in comparison to 20% in Industrialised countries (Shaw, Sicree, & Zimmet, 2010).

Body weight, adipose deposits, ectopic organ fat

Weight gain (Ng et al., 2014) and an unhealthy diet and lifestyle (Temelkova-Kurktschiev & Stefanov, 2012) have been identified as the most significant risk factors for developing T2D. They lead to compromised energy homeostasis and lipo-regulation which may adversely promote the accumulation of fat in metabolically 'risky' deep subcutaneous and visceral compartments rather than 'safe' superficial subcutaneous adipose compartments (Chen et al., 2018; Tene et al., 2018). Increased visceral adiposity - particularly non-adipose ectopic deposition into key organs such as pancreas and liver - may alter normal physiological control and worsen insulin resistance (IR) and pancreatic β -cell dysfunction thereby worsening risk of T2D (Hocking, Samocha-Bonet, Milner, Greenfield, & Chisholm, 2013; Sattar & Gill, 2014).

Accordingly, ongoing strategies to manage T2D are aimed at diet and lifestyle changes. Several International T2D prevention trials (Christensen et al., 2018; DiabetesPreventionProgramResearchGroup, 2002; Li et al., 2008; Lindström et al., 2006; Ramachandran et al., 2006) have shown that implementing lifestyle interventions in high-risk individuals can prevent or at least delay the progression to T2D by 50% (Liu, Silvestre, & Poppitt, 2015). Diets characterised by both greater quantities and variety of plant-origin foods have been shown to improve glucose tolerance and decrease T2D risk (McMacken & Shah, 2017). While the precise mechanism by which they exert their beneficial effects are unknown (Kim, Quon, &

Kim, 2014), the ubiquitous polyphenolic phytochemicals contained within plants have been proposed to contribute to the delay in T2D progression (Dembinska-Kiec, Mykkänen, Kiec-Wilk, & Mykkänen, 2008).

Plant based whole fruit extract

Ubiquitous dietary phytochemicals or polyphenols, consumed as part of fruit and or their extract, have long since been recognised to have a role in ameliorating T2D risk (Xiao & Hogger, 2015). Numerous randomised control trials (RCTs) using plant-based dietary polyphenol rich products, consumed over 4 -12 week duration (Balzer et al., 2008; Bozzetto et al., 2015; Kar, Laight, Rooprai, Shaw, & Cummings, 2009; Mellor, Madden, Smith, Kilpatrick, & Atkin, 2013; Ochiai et al., 2014; Ogawa, Matsumae, Kataoka, Yazaki, & Yamaguchi, 2013; Rakvaag & Dragsted, 2016; Zibadi, Rohdewald, Park, & Watson, 2008), have been shown to significantly improve inflammation, glycaemia and oxidative stress associated with T2D.

Recent characterisation of New Zealand grown cultivars of feijoa (Apollo, Unique, Opal Star, and Wiki Tu) shows they are abundantly rich in phenolic compounds, particularly procyanidins B1 & B2, catechins and quercetin-3-galactoside (Y. Peng, Bishop, Zhang, Chen, & Quek, 2020). Benefits associated with consumption of feijoa (*Acca sellowiana* (O.Berg) Burret) have been attributed to its antimicrobial (Elfarnini, Abdel-hamid, Achir, Jamaledine, & Blaghen, 2018; Smeriglio et al., 2019), antioxidant (Yaoyao Peng, Bishop, & Quek, 2019) and anti-inflammatory (Yaoyao Peng, Bishop, Ferguson, & Quek, 2018) properties. Feijoa whole fruit powder is commercially available in NZ as Feiolix® (<https://feiolix.com/>) under the Food Act 2014. The powder is rich in phenols and fibre (Cooney J. & Trower, 2015) as well as novel abscisic acid (ABA) (Zocchi et al., 2017) which is known to upregulate peroxisome proliferator-activated receptor (PPAR γ) to stimulate insulin secretion, glucose absorption and glucagon peptide like 1 (GLP-1) secretion (Bassaganya-Riera et al., 2011).

Administration of Feiolix® over a 16-week period in leptin deficient (ob-/ob-) mice significantly reduced weight gain, feed efficiency ratio, liver weight and cholesterol levels (Foo & Watson, 2015). In a RCT in 34 individuals with type 2 diabetes and mild to moderate hypertension the consumption of 150 mg/d, over a 12 week period, showed a significant decrease in blood pressure, fasting plasma glucose (FPG), glycosylated haemoglobin (HbA_{1c}), triglycerides (TAG), total cholesterol (TC) and low density lipoprotein (LDL-C)] in comparison to placebo (Taghavi, Hoseini, Panah, Masud, & Watson, 2012). The recommended daily dose is 1150 mg/d with high dose considered at 2300 mg/d calculated on the basis of total polyphenols by UV responsive molecules (UVRM) relative to the UVRM of 150 mg powder. The dose of 1150 mg/d was shown to be as efficacious in lowering blood glucose and TAG at 3 weeks, as the high dose, in a streptozotocin (STZ)-induced diabetes mouse model (unpublished data).

Glycaemic response to diet

The response to diet/dietary components, in particular the postprandial glucose response, remains poorly characterised in those at risk of T2D; despite postprandial response being clearly linked as an independent risk factor for development of T2D (AmericanDiabetesAssociation, 2015) and CVD (Gallwitz, 2009). There is growing evidence that glycaemic response of individuals to a dietary intervention is both highly variable and difficult to predict (Christinat, Valsesia, & Masoodi, 2020; Valsesia et al., 2020; Zeevi et al., 2015). Hence, predicting response and in turn personalising intervention diets to optimise glycaemic improvements in high risk individuals is a key next step in development of food and beverage products for amelioration of dysglycaemia and T2D.

Building on PANAMAH programme outcomes

In Tranche 1 our research team phenotyped a unique cohort of Chinese and Caucasian adults resident in Auckland, New Zealand in the *Thin on the Outside Fat on the Inside* (TOFI)_Asia study. In this study we observed a significantly worse profile of clinical risk biomarkers in the Chinese cohort when compared with a similar age and BMI-matched Caucasian cohort confirming that they were at worse risk and likely to develop T2D earlier than their Caucasian counterparts. Importantly, we also identified metabolomic biomarkers of prediabetes which may represent early biomarkers of disease, and noted the characteristic pattern of lipid ‘overspill’ into pancreas and liver in a sub-cohort of women who underwent magnetic resonance imaging (MRI) for pancreas fat and magnetic resonance spectroscopy(MRS) to identify liver fat.

Tranche 2 is investigating nutrition interventions to ameliorate T2D risk in carefully phenotyped lean and overweight individuals with pre-diabetes resident within New Zealand. Recent studies have shown that greatest success can be achieved when long-term dietary intervention for better glycaemic control is preceded by prior body weight and adipose mass loss. Identifying dietary components that can contribute to this long-term weight loss maintenance and hence improve glycaemic endpoints is key to this. In addition, evidence is building in support of personalised diets where glycaemic response to intervention (*personalised postprandial glucose response, PPGR*) may be predicted through integration of factors such as dietary intake, blood parameters including continuous glucose monitoring (CGM) and serum metabolome, faecal microbiome, and physical activity. (Zeevi et al., 2015) Our research program will further build on the PPGR algorithms proposed by Zeevi, Segal and colleagues, using a wider set of parameters including detailed body composition and ectopic organ fat and metabolomics data.

Systems nutrition and PPGR

Previously the PANaMAH programme has focused on shorter-term F&B interventions, in small cohorts of individuals, and interventions with no weight loss component and a 'one-size-fits-all' approach. The Evaluating FEijoa foR Dlabetes Prevention in a Multi-ethnic New ZeAlaND Cohort_(FERDINAND) study builds on the previous HVN programme, and significantly extends into a longer-term 6 month intervention in larger cohorts of at risk adults. The aim of the programme is to use a systems nutrition approach (demographics, anthropometry, clinical biomarkers and 'omics platforms-metabolomics, genomics/faecal microbiome; to predict personalised postprandial glucose response, PPGR) to evaluate whether commercially available feijoa whole fruit powder (Feiolix®) can contribute to improved glycaemia during both (i) short-term body weight loss, and (ii) longer-term weight loss maintenance.

